#### **4.5.5 Concomitant Medications**

*The definition of concomitant medications, as well as permitted and prohibited medications is described in Section 4.4. Concomitant medications used by a patient from 4 weeks prior to initiation of emicizumab to the Study Completion/Early Termination Visit (or the Safety Follow-up Visit, if applicable) should be reported to the investigator and recorded on the Concomitant Medications eCRF.*

*Any hemostatic medications (e.g. bypassing agents) and other medications used to treat or prevent bleeds in the 6-month period prior to starting emicizumab treatment will also be collected. Treatments for bleeds (i.e., bypassing agents and other medications to treat bleeds), will be collected in the bleed records.*

#### **4.5.6 Laboratory, Biomarker, and Other Biological Samples**

Central laboratory assessments will be performed as indicated (see Table 9). *Unless otherwise specified, additional analysis may be performed at a local laboratory, as per the investigator's discretion. Any additional laboratory results which are required as part of the patient's safety assessment should be recorded in the unscheduled visit eCRFs. Central labs are part of the non-eCRF data which will be sent to the Sponsor directly by the central lab vendor.*

**On treatment days, blood collection should occur within 2 hours prior to emicizumab administration unless otherwise specified.**

Table 10 Central vs Local Laboratory Assessments

Sample	Laboratory
--------	------------

Sample	Laboratory
Hematology and blood chemistry	Central
Pregnancy tests	Local
HIV and hepatitis serology	Local
Anti-FVIII antibodies	Central
Anti-emicizumab antibodies	Central
Pharmacokinetic samples	Central
Safety biomarkers	Central
Safety coagulation system biomarkers	Central
PD biomarkers	Central
Bone and joint biomarkers	Central
Extra testing with use of bypass agents	Central

#### **4.5.6.1 Hematology and Blood Chemistry**

*Hematology and blood chemistry tests include:*

- Hematology (hemoglobin, hematocrit, platelet count, red blood cell [RBC] count, white blood cell [WBC] count, absolute or non-absolute differential count [neutrophils, eosinophils, lymphocytes, monocytes, basophils, and other cells], mean corpuscular volume, mean corpuscular hemoglobin, mean corpuscular hemoglobin concentration, RBC distribution width, prothrombin time [PT] in seconds, and international normalized ratio [INR; the PT/INR ratio will be calculated])
- Serum chemistry (sodium, potassium, chloride, glucose, blood urea nitrogen (BUN), creatinine, calcium, phosphorus, magnesium, total and direct bilirubin, total protein, albumin, ALT, AST, *lactate dehydrogenase* (LDH), alkaline phosphatase, and creatine phosphokinase)

*Laboratory assessments completed during Screening do not have to be repeated at Week 1, if the period between Screening and Week 1 is  $\leq 5$  days and there has been no change in the patient's health status as assessed by the investigator.*

*Samples will be sent to the central laboratory for analysis.*

#### **4.5.6.2 Pregnancy Tests**

*Female patients of childbearing potential (including those who have had a tubal ligation) will be required to have a negative serum pregnancy test result during Screening, and again within 7 days prior to the first dose of emicizumab. Urine pregnancy tests will be performed throughout the study treatment period. Pregnancy testing will be conducted at the local laboratory.*

#### **4.5.6.3 HIV and Hepatitis Serology**

The specific tests utilized for hepatitis and HIV testing are per local standard of care. As this patient population is at high risk for HIV, hepatitis A, B and C, sites should consider testing for these. While the specific serological tests used is at the discretion of the Investigator, this is with the understanding that the status of that participants' hepatitis or HIV is confidently known at time at enrollment. HIV and hepatitis serology tests will be conducted at the local laboratory.

#### **4.5.6.4 Anti-FVIII Antibodies**

For the assessment of anti-FVIII antibodies (inhibitors), functional assays that utilize a clotting readout (classic Bethesda or Nijmegen assay) cannot be used for patients on emicizumab therapy as emicizumab drives clotting even in the presence of FVIII inhibitors, causing a false-negative test result (see [Section 5.1.3](#)). After the first dose, local measurement of FVIII inhibitors, if indicated, requires use of an ELISA-based test or a chromogenic Bethesda assay.

At the discretion of the local investigator, any additional urgent requests to assess FVIII inhibitors will need to be sent to the central laboratory (see [Appendix 2](#)

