### 5.1.3 Interpretation of Coagulation Assays for Patients Receiving Emicizumab

Emicizumab interacts with standard laboratory assays used in the management of patients with hemophilia A (see Table 11). In one-stage assays, emicizumab is associated with a supra-physiologically short time to clot formation and thus normalization of aPTT at sub-therapeutic levels. Emicizumab is not recognized or neutralized by FVIII inhibitors, and therefore *FVIII inhibitors cannot be detected in the presence of emicizumab* by functional tests such as Bethesda or Nijmegen-Bethesda assays, which use a one-stage clotting-based readout. Emicizumab activity cannot be detected by chromogenic assays using purified bovine coagulation proteins, thus *chromogenic Bethesda assays using bovine proteins can be used to measure FVIII inhibitor titer in the presence of emicizumab*. Emicizumab activity can be detected using *chromogenic assays* composed of human proteins. See the Investigator's Brochure for additional details on which tests can be used and how the test results can be interpreted.

**Table 12** *Coagulation Test Results Affected and Unaffected by Emicizumab*

Results Affected by Emicizumab	Results Unaffected by Emicizumab
aPTT Bethesda assays (clotting-based) for FVIII inhibitor titers One-stage, aPTT-based, single-factor assays aPTT-based Activated Protein C Resistance Activated clotting time	Bethesda assays (bovine chromogenic) for FVIII inhibitor titers Thrombin time One-stage, prothrombin time-based, single-factor assays Chromogenic-based single-factor assays other than FVIII [a] Immuno-based assays (i.e., ELISA, turbidimetric methods) Genetic tests of coagulation factors (e.g., Factor V Leiden, Prothrombin 20210)

*ELISA = enzyme-linked immunosorbent assay*

a. *For important considerations regarding FVIII chromogenic activity assays, see Drug Interactions listed in the US Package Insert*

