- i. **Hematology and blood chemistry** assessments will include a complete blood count with differential and serum chemistries (see Section 4.5.6.1). Laboratory assessments completed during Screening do not have to be repeated at Week 1, if the period between Screening and Week 1 is  $\leq 5$  days and there has been no change in the patient's health status as assessed by the investigator. Samples will be sent to the central laboratory for analysis.
- j. **Pregnancy tests:** Female patients of childbearing potential (including those who have had a tubal ligation) will be required to have a negative serum pregnancy test result during Screening and again within 7 days prior to the first dose of emicizumab. Urine pregnancy tests will be performed throughout the study treatment period. Pregnancy testing will be conducted at the local laboratory.
- k. The specific tests utilized for **hepatitis and HIV serology** testing are per local standard of care. As this patient population is at high risk for HIV, hepatitis A, B and C, sites should consider testing for these. While the specific serological tests used is at the discretion of the Investigator, this is with the understanding that the status of that participants' hepatitis or HIV is confidently known at time at enrollment. HIV and hepatitis serology tests will be conducted at the local laboratory.
- l. For the assessment of **anti-FVIII antibodies** (inhibitors), functional assays that utilize a clotting readout (classic Bethesda or Nijmegen assay) cannot be used for patients on emicizumab therapy as emicizumab drives clotting even in the presence of FVIII inhibitors, causing a false-negative test result (see Section 5.1.3). After the first dose, local measurement of FVIII inhibitors, if indicated, requires use of an ELISA-based test or a chromogenic Bethesda assay. At the discretion of the local investigator, any additional urgent request to assess FVIII inhibitors will need to be sent to the central laboratory (see Appendix 2 for additional information). Plasma samples for anti-FVIII antibodies will be analysed at the central laboratory
- m. Plasma samples are required for immunogenicity assessments to detect **anti-emicizumab antibodies**. Additional samples to detect anti-emicizumab antibodies may also be drawn at the time of hypersensitivity events or following suspected loss of efficacy. Samples will be analysed at the central laboratory.

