**Table 2: List of analyzed biomarkers**

Factor VIII Inhibitor, chromogenic	CBU
Factor VIII Activity, chromogenic	U/dL
Activated Partial Thromboplastin Time	sec
D-Dimer	ug/mL (FEU)
Factor IX, concentration	ug/mL
Factor X, concentration	ug/mL
Prothrombin fragment 1+2	ng/mL
Prothrombin INR	Fraction of 1
Fibrinogen	g/L

All parameters are quantitative

Outputs to be produced for selected biomarkers and FVIII inhibitor titer are as follows (Table 3: List of outputs to be generated for biomarkers and FVIII inhibitor titers). Additional detail for each lab parameter is provided below.

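### The rule for local on-treatment inhibitor tests accepts any chromogenic Bethesda assay, but protocol 5.1.3 clears only the bovine version

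*Protocol*

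**What the plan says.** Protocol 4.5.6.4 bars clotting-based inhibitor assays in patients on treatment because "emicizumab drives clotting even in the presence of FVIII inhibitors, causing a false-negative test result". That sentence points to 5.1.3. The next one gives the operative rule for sites: after the first dose, "local measurement of FVIII inhibitors, if indicated, requires use of an ELISA-based test or a chromogenic Bethesda assay". The anti-FVIII antibodies footnote to protocol Appendix 1 repeats it ("requires use of an ELISA-based test or a chromogenic Bethesda assay"), and SAP Appendix 2, footnote k, uses the same words. None of the three names a reagent species.

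Protocol 5.1.3 separates chromogenic assays by reagent. For bovine reagents it says "Emicizumab activity cannot be detected by chromogenic assays using purified bovine coagulation proteins", and concludes that "chromogenic Bethesda assays using bovine proteins can be used to measure FVIII inhibitor titer in the presence of emicizumab". For human reagents it says "Emicizumab activity can be detected using *chromogenic assays* composed of human proteins". It also says that FVIII inhibitors neither recognise nor neutralise emicizumab. Its table of affected and unaffected tests (headed Table 12, cited in the text as Table 11) has one Bethesda entry in the unaffected column: "Bethesda assays (bovine chromogenic) for FVIII inhibitor titers".

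SAP 4.10, Table 2, lists "Factor VIII Inhibitor, chromogenic" and a chromogenic FVIII activity row, again without species.

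**The concern.** The rule exists to stop one specific error: an inhibitor reported as absent because the assay is reading emicizumab. It closes the clotting-assay route to that error. It then admits a class of assay that 5.1.3 splits in two, one half blind to emicizumab and the other half responsive to it. A site that reads 4.5.6.4 or the schedule footnote and uses a human-reagent chromogenic kit has complied with the protocol, yet may hold a result that 5.1.3 gives it no reason to trust.

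At stake is whether an individual local titer obtained during treatment can be believed. A falsely low or negative value could be taken to mean that the inhibitor has declined or gone. The concern is about whether the passages agree. It does not reach the sample size, an error rate or an endpoint.

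**Working it through.** No arithmetic applies, and the plan states no figure on this point. The check sets the passages side by side.

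| Test on a patient receiving emicizumab | Allowed locally by 4.5.6.4? | What 5.1.3 says |
|---|---|---|
| Clotting-based Bethesda | No | Affected |
| ELISA-based | Yes | Unaffected (immuno-based assays) |
| Chromogenic Bethesda, bovine reagents | Yes | Unaffected |
| Chromogenic Bethesda, human reagents | Yes, because no species is given | Not listed as unaffected; human-protein chromogenic assays detect emicizumab |

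Only the last row is out of line. The reasoning from there is:

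1. Protocol 4.5.6.4 explains why the clotting version fails: the readout responds to emicizumab even when an inhibitor is present, so the inhibitor is missed.
2. Two conditions produce that failure. The readout must respond to emicizumab, and the inhibitor must leave emicizumab's activity intact.
3. Section 5.1.3 supplies the first condition for chromogenic assays with human proteins.
4. Section 5.1.3 supplies the second for any assay, since inhibitors do not neutralise the drug.
5. So a Bethesda test with a human-protein chromogenic readout meets both conditions. The titer can be understated or read as negative.

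Step 5 is an inference. No passage says outright that a human-reagent chromogenic Bethesda test gives a false negative, and none says that any site uses one. The supported wording is therefore that such a test can mislead.

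Exposure is bounded as follows:

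- The central-versus-local laboratory table in protocol 4.5.6 and the closing line of 4.5.6.4 send study anti-FVIII samples to the central laboratory.
- Protocol 4.5.6.4 also sends additional urgent requests there.
- What is left is the optional local test that 4.5.6.4 allows when indicated, at a site that uses neither ELISA nor bovine reagents.
- Inhibitor titer is not among the objectives and endpoints in protocol section 2. In SAP 4.10 it appears only in descriptive biomarker outputs.

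**The case against.** The strongest reply is that this is a general statement followed up by a cross-reference, and not a contradiction. The sentence before the rule sends the reader to 5.1.3, and the two footnotes carry the same reference. Anyone who follows it finds the bovine restriction in the text and in the table. Most of the harm is also routed away, because study samples and urgent requests go to the central laboratory.

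Much of that stands and sets the size of the point. It does not remove it. The cross-reference is attached to the statement about clotting assays. The sentence that tells a site which assays qualify carries neither the restriction nor a link, and its mandatory wording reads as complete. In the SAP footnote the copied reference gives 5.1.3 without naming the protocol, and the SAP has no such section.

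A reader might be tempted by four stronger readings, which the documents do not support:

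- That all local on-treatment inhibitor tests are compromised. They are not, since 5.1.3 treats ELISA and bovine chromogenic tests as unaffected.
- That the number of sites at risk can be estimated. The documents say nothing about which kits sites hold, so any share would be a guess.
- That the study's own titers will show an artificial fall on treatment. That would need the central laboratory to use human reagents for the titer. Nothing suggests this, and the protocol itself identifies bovine reagents as usable.
- That FVIII activity from human and bovine reagents will be pooled. SAP Table 2 lists one chromogenic activity row, separate from the inhibitor row, and nothing indicates that two versions are run.

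**Conclusion.** The point holds as an inconsistency with a narrow practical reach. Protocol 4.5.6.4 and the two footnotes permit a test that 5.1.3 does not clear and that, on 5.1.3's own statements, can give the false-negative result the rule is meant to prevent.

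Its size is qualitative. The documents give neither the number of optional local tests nor the reagents used. The number affected could be anything from none, if every local test is ELISA or bovine, up to all the optional local tests run by a non-bovine chromogenic Bethesda method. The primary safety analysis and the bleed analyses are untouched.

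The conclusion rests on reading 5.1.3's statement about human-protein chromogenic assays as applying to a Bethesda test with that readout. The protocol's own reasoning about clotting assays supports that reading, but no passage states it.

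The missing species in SAP Table 2 is a gap in labelling and is not evidence of an unsuitable central assay. It still deserves filling. By 5.1.3, the species decides whether a chromogenic FVIII activity value includes emicizumab's effect, and whether a reader can take the inhibitor titer at face value.

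**What to change.** Reconcile the three passages with 5.1.3 by carrying over the protocol's own qualifier. In protocol 4.5.6.4, the Appendix 1 anti-FVIII antibodies footnote and SAP Appendix 2 footnote k, write *a bovine chromogenic Bethesda assay*. The ELISA option stays as it is. In the SAP footnote, name the protocol in the reference to 5.1.3.

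In SAP Table 2, state the reagent species for the chromogenic FVIII inhibitor and chromogenic FVIII activity rows, taken from the central laboratory's actual methods.

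The cost is one word in three places, two table labels and a short memo to sites. A site without a bovine kit loses nothing essential, since ELISA and the central laboratory are both already provided for in 4.5.6.4. No sample size, endpoint or planned analysis changes.

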#### **Schedule of Biomarker Samples**

for additional information).

Plasma samples for anti-FVIII antibodies will be analysed at the central laboratory.

#### **4.5.6.5 Anti-emicizumab Antibodies**

Plasma samples are required for immunogenicity assessments to detect anti-emicizumab antibodies. Additional samples to detect anti-emicizumab antibodies may also be drawn at the time of hypersensitivity events or following suspected loss of efficacy. Samples will be analysed at the central laboratory.

#### **4.5.6.6 Pharmacokinetics**

Plasma samples are required for PK assessments. On days where PK samples are to be collected, the emicizumab injection will be performed in the clinical unit. One single pre-dose sample is required on the applicable visits. Samples will be analysed by the central laboratory.

#### **4.5.6.7 Biomarkers**

##### **4.5.6.7.1 Safety Biomarkers**

Plasma samples for safety biomarker assessment must be citrate plasma. Tests may include, but are not limited to, D-dimer. Samples will be analysed by the central laboratory. See [Appendix 2](#).

##### **4.5.6.7.2 Safety Coagulation System Biomarkers**

Plasma samples for safety coagulation system biomarker assessment must be citrate plasma. Tests include FVIII:Ag, FIX:Ag and FX:Ag. Samples will be analysed by the central laboratory. See [Appendix 2](#).

#### **4.5.6.7.3 PD Biomarkers**

*Plasma samples for PD biomarker assessment must be citrate plasma. Tests will include, but are not limited to FVIII activity and modified aPTT (one stage). Additional plasma samples will be collected for future exploratory research, which may include tests such as CWA and others (see [Appendix 2](#)). Samples will be analysed by the central laboratory.*

#### **4.5.6.7.4 Bone and Joint Biomarkers**

*Serum and plasma ethylenediaminetetraacetic acid (EDTA) samples for bone and joint biomarkers must be collected after fasting (no food or drink other than water for at least 8 hours prior to the blood draw). Ideally these samples should be collected in the morning (before noon), in order to control for diurnal variation. Please consult the Central Laboratory Services Manual for details. The selection of exploratory bone and joint biomarkers to be tested will build on findings from biomarker analyses in other emicizumab trials and may include C-terminal telopeptide of collagen 1 (CTX-1), osteoprotegerin (OPG), procollagen type 1 amino-terminal propeptide (PINP), and soluble receptor activator of nuclear factor kappa-B ligand (RANK-L) (see [Appendix 2](#)*

#### **Schedule of Biomarker Samples**

*). Samples will be analysed by the central laboratory.*

#### **4.5.6.8 Extra Testing with Use of Bypass Agents**

In the event of a breakthrough bleed that is treated with bypassing agents, it is recommended that the following laboratory tests will be performed within 24–48 hours of initial bypassing agent use (these tests will be conducted so that the investigator can monitor the patient for potential thromboembolic events and *microangiopathic hemolytic anemia* or TMA). *These tests include:*

- Platelet count
- Serum creatinine
- LDH
- Schistocytes
- A plasma sample should also be provided for central laboratory monitoring of prothrombin fragment F1+2, fibrinogen and D-dimer.

*Ideally, samples for these tests should be analysed at the central laboratory. Exceptionally in urgent situations where results are required quickly, local laboratory testing can be used, with results recorded in the eCRF.*

For patients who require multiple doses of bypassing agents, laboratory monitoring should be performed every 24–48 hours until 24–48 hours after the last dose of bypassing agents is administered to treat a specific bleed. *All laboratory results which are required as part of the patient's safety assessment should be recorded in the unscheduled visit eCRFs.*

#### **4.5.6.9 Sampling Procedures and Sample Storage, Shipment and Destruction**

For sampling procedures, storage conditions, and shipment instructions, see the *Central Laboratory Services Manual*.

Biological samples will be destroyed when the final Clinical Study Report has been completed, with the following exceptions:

- Plasma or serum samples, as applicable, collected for anti-FVIII antibody, PD biomarker, safety biomarker, safety coagulation system biomarker, bone and joint biomarker assessments *and other future exploratory research* will be destroyed no later than 5 years after the final Clinical Study Report has been completed.

When a patient withdraws from the study, samples collected prior to the date of withdrawal may still be analyzed, unless the patient specifically requests that the samples be destroyed or local laws require destruction of the samples.

Data arising from sample analysis will be subject to the confidentiality standards described in [Section 8.4](#).

#### **4.5.7 Bleed Assessments**

*Patients will be trained on how to record their bleeds and hemophilia medication use using an ePRO device where possible. When bleeds occur, patients will need to record the site of bleed, type of bleed, time of each individual bleed (day, start and stop time), and treatment for bleed. At least once a week, patients will need to record any hemophilia medication use (including emicizumab) and information regarding any bleeding events. Investigator review of patient-reported bleed/medication records with the patient/caregiver will occur for completeness and accuracy throughout the study.*

##### **4.5.7.1 Definition of a Bleed**

For the purposes of the efficacy analyses, a standardized definition of bleed, adapted from the standard criteria defined by the FVIII and FIX Subcommittee of the Scientific and Standardization Committee (SSC) of the International Society on Thrombosis and Haemostasis (ISTH), that is similar to the definition used in a recent clinical investigation, will be utilized in this study ([Blanchette et al. 2014](#); [Mahlangu et al. 2014](#)):

- An event is considered a bleed if coagulation factors are administered to treat signs or symptoms of bleeding (pain, swelling, etc.). An additional definition of all reported bleeds (irrespective of treatment with coagulation factors) will be applied for a separate analysis.
- Bleeds starting from the first sign of a bleed and ending 72 hours after the last treatment for the bleed, which have any symptoms of bleeding at the same location or injections are  $\leq 72$  hours apart, are considered the same bleed.
- Any injection to treat the bleed, taken  $> 72$  hours after the preceding injection, is considered the first injection to treat a new bleed at the same location.
- In case of trauma with multiple different locations of bleed, this will be considered as one bleed for the analyses. However, all data will be collected, including the various locations of the different bleeds.
- Any bleed with a different etiology is considered a separate bleed regardless of time from last injection.

